## 14.0 ANALYSIS

### Methods

All analyses will be performed from the intention-to-treat principle, for all participants studied together and stratified by sex and age group.

#### Primary outcome:

Mean change in GMT in samples from day 14 and 42 will be compared between the control group and the three treatment groups in linear regression analyses with adjustment for baseline level of GMT, age group, and sex. In case residuals are not normally distributed, the analysis will be performed on log-10 transformed change in GMT instead. The proportion of participants who seroconvert will be compared in logistic regression analysis with adjustment for age group and sex.

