## 10.0 STUDY METHODS

### Trial design

A single-blinded, placebo controlled, randomized clinical trial, with nested immunological studies. Participants are randomized 1:1:1:1 to four groups: BCG 14 days before, together with, or 14 days after IIV compared to placebo.

People  $\geq 65$  years of age who plan to accept the offer of seasonal influenza vaccination are eligible for participation.

Participants are vaccinated once at day 0 and twice at day 14 (one shot in each arm). All participants receive the standard seasonal IIV recommended by the Danish Board of Health. The participants will come back for a follow-up interview at day 42 and all are followed for six months post-randomization with electronic questionnaires about their health. These include information on symptoms and disease, potential side effects, other vaccinations, visits to general practitioner or on call doctor, and hospitalizations. Every survey period is 14 days, starting from day 0 (inclusion).

Blood samples for influenza antibody testing are collected from all participants at day 14 and 42. Samples for further immunological analyses are collected from subgroups at day 0, day 14, day 21, and day 42.

Vaccination schedule:

Group	Day 0 (one shot)	Day 14 (two shots)	Day 42
1	BCG	IIV + Placebo	Follow up visit
2 (Control)	Placebo	IIV + Placebo	Follow up visit
3	Placebo	IIV + BCG	Follow up visit
4	IIV	Placebo + BCG	Follow up visit

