### **Sample size**

We aim to include 75 participants in each group, 300 in total. With an anticipated seroconversion rate of 50% in the control group, we should be able to show a 30% increase in seroconversion rate associated with BCG vaccine with 80% power and an alpha of 0.05, anticipating 10% loss to follow-up.

All participants are followed for clinical symptoms for six months. With this sample size, we will only be able to show differences in clinical symptoms if such differences are pronounced.

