## **13.0 DESCRIPTION OF OUTCOMES AND VARIABLES**

### **Primary outcome**

Change in antibody levels to influenza virus strains included in the IIV, comparing levels at day 14 and day 42; just before and 4 weeks after influenza vaccination (for group 4, it will be 2 and 6 weeks after influenza vaccination).

We will use *Influvactetra* (Mylan ApS, Copenhagen), a quadrivalent inactivated influenza vaccine containing the following strains:

1. A/Victoria/2570/2019, IVR-215 (H1N1, pdm09-like strain)
2. A/Cambodia/e0826360/2020, IVR-224 (H3N2-strain)
3. B/Washington/02/2019, wild type
4. B/Phuket/3073/2013, wild type

Influenza antibodies are measured in hemagglutination-inhibition assay (HAI) yielding dilution titers with an expected range of <20 to 320 for this population. Geometric mean titers (GMT) will be determined by calculating the mean of the log-transformed duplicate titers followed by back transformation (calculated as  $10^x$ , where x is defined as the mean log-transformed titer).

Seroconversion is defined as a pre-vaccination HAI titer <10 and a post-vaccination titer  $\geq 40$ , or a pre-vaccination titer  $\geq 10$  and a minimum four-fold rise in post-vaccination titer.

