**List of variables:**

Variable name	Definition	Type	Scale
Primary outcome: Change in antibody levels to influenza virus strains included in the IIV, comparing levels at day 14 and day 42.			
ab_diff_strain	Influenza antibody titer (GMT) day 42 minus day 14. For each strain.	Continuous	<20 to 320
seroconv	Seroconverted after influenza vaccination (4-fold increase in Ab titer). For each strain.	Binary	0: no 1: yes
Secondary outcome, self-reported infections:			
infection	Infection or symptoms consistent with infection (0 or 1 every survey period).	Binary	0: no 1: yes
Secondary exposure:			
ab_day42_cat	Influenza ab titer day 42 (GMT). Secondary exposure.	Categorical	1. quartile 2. quartile 3. quartile 4. quartile
Secondary outcome, immunological:			
b_lymph	Number of activated B-cells. For all relevant subtypes.	Continuous	0.0-0.3 x 10  /L

cytokine_stim_day	Cytokine concentration (TNF $\alpha$ , IL-1 $\beta$ , IFN- $\gamma$ ) after stimulation with: Poly(I:C), Pam3CSK4, LPS, and influenza vaccine at the various timepoints (day 0, 14, and 42).	Continuous	0-1500 pg/mL
diff_cytokine_stim_day	Fold change in cytokine concentration from baseline value (day 0) to day 14 and 42 after stimulation with various stimuli. Compared between the randomization groups. Using randomization group as exposure (categorical).	Continuous	0-10

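### The Part B fallback analysis takes log10 of a titre difference, which is undefined for a flat or falling titre and is not a fold rise; no handling is stated

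*SAP*

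**What the plan says.** All references are to SAP Part B.

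- **Outcome variable (section 13.0, List of variables).** ab_diff_strain is "Influenza antibody titer (GMT) day 42 minus day 14. For each strain". Its scale is listed as <20 to 320.
- **Lead model (section 14.0, Primary outcome).** The mean change is compared between control and each of the three BCG groups by linear regression, with baseline titre, age group and sex as covariates.
- **Fallback (same place).** "In case residuals are not normally distributed, the analysis will be performed on log-10 transformed change in GMT instead". No test, threshold or per-strain rule for the switch is given.
- **Use of logs (section 13.0, Primary outcome).** Logs serve to average the duplicate readings, "where x is defined as the mean log-transformed titer". The average is then back-transformed, so the change is taken between titres.
- **Assay range (same place).** The assay is described as "yielding dilution titers with an expected range of <20 to 320 for this population".
- **Exclusions (section 14.0, Missing data).** Only participants with an absent or unusable sample leave the antibody analysis. The Methods paragraph of the same section sets intention-to-treat for all analyses.
- **Sampling times.** "Blood samples for influenza antibody testing are collected from all participants at day 14 and 42" (section 10.0). Section 13.0 adds "for group 4, it will be 2 and 6 weeks after influenza vaccination".

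**The concern.** A logarithm exists only for positive numbers. With the change defined as a subtraction, a participant with no rise has log10(0) and one with a fall has the log of a negative number. The analyst who follows the text literally must either drop these participants, which selects on the outcome and conflicts with intention-to-treat, or add a constant that nobody planned.

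The fallback may well become the operative analysis, because differences between dilution titres tend to be right-skewed. The transformed quantity also changes meaning: it rewards a high starting titre and no longer measures the relative rise on which the SAP's own seroconversion rule rests. At stake are the size and interpretation of one of the two primary variables in Part B.

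**Working it through.** The SAP states no figure for this point, so there is none to reproduce. The check has three steps.

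**1. Is the transformation defined?** Inputs: the subtraction in the variable list and the range <20 to 320. Assumption: two-fold dilutions, with <20 taken as 10, giving 10, 20, 40, 80, 160, 320.

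- Possible pairs (day 14, day 42): 6 × 6 = 36.
- Zero change: 6. Negative change: 15. Undefined: 6 + 15 = 21 of 36. This counts possible pairs; it is not an expected frequency.
- Range of the difference: 10 − 320 = −310 to 320 − 10 = +310. The scale listed for ab_diff_strain is the range of a titre, not of a difference.

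**2. Where defined, is it a fold rise?**

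| Day 14 | Day 42 | log10(day 42 − day 14) | log10(day 42 / day 14) |
|---|---|---|---|
| 10 | 40 | log10(30) = 1.48 | 0.602 |
| 20 | 80 | log10(60) = 1.78 | 0.602 |
| 80 | 320 | log10(240) = 2.38 | 0.602 |
| 160 | 160 | undefined | 0 |
| 160 | 80 | undefined | −0.301 |

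Three equal four-fold rises receive three different values. The log ratio gives one value for all of them and is defined in every row.

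**3. How much could it matter?** Illustrative only. From section 10.0: 75 per group less 10% is about 68; "With an anticipated seroconversion rate of 50% in the control group"; a 30% increase read as relative gives 50% × 1.3 = 65%, and read as absolute gives 80%. Assumed: baseline log2(titre/10) Normal(1.5, 1.3); SD of the log2 rise 1.2 or 1.5; single or duplicate readings; <20 coded 5 or 10; upper cap none or 320. This makes 16 scenarios. The mean rise is solved to give the seroconversion rates. The two arms stand for group 1 or 3 against control.

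- *No effect:* type I error 4.2–6.7% with undefined values dropped.
- *65%, undefined values:* change ≤ 0 in about 13–26% of controls and 7–16% of treated.
- *65%, power:* about 25–38% with those values dropped; 55–61% for a log-titre model on everyone; 28–32% for the planned raw difference if titres are uncapped, 45–51% if capped at 320.
- *65%, geometric mean ratio:* 1.35–1.55 from the log-titre model on everyone, 1.21–1.33 from the same model limited to participants with a rise.
- *65%, added constant c, log10(max(change, 0) + c):* power 49–56%, but the ratio is 1.71–2.07 for c = 1, 1.43–1.60 for c = 10 and 1.26–1.37 for c = 40.
- *80%, power:* 86–97% with values dropped, about 100% for the log-titre model, 80–87% (uncapped) or 99% (capped) for the raw difference.
- *Trigger:* at 65%, residuals of the raw difference fail a Shapiro-Wilk test at 5% in at least 99.8% of simulated trials; at 80%, in 93–100%.

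**Group 4.** Its day-14 sample is already two weeks after influenza vaccination. If the mean further rise to day 42 is 0 to 0.5 log2 units (assumed), about 50–78% of its values are undefined, against 13–26% of controls.

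**The case against.** The best defence is that the authors meant change in log10 titre. They already average duplicates on the log10 scale, the literal version visibly fails for ties, and the subtraction in the variable list may describe only the untransformed variable. This is plausible, and a competent analyst might well take that route. But the words used transform the change, the antibody variable is a subtraction, and the variable list uses fold change for cytokines and not for antibodies. The plan should not leave that choice open until the data are seen.

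Three further points stand in part:

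- *Power.* The wide gap is measured against a log-titre model that the SAP does not plan. Against its own lead analysis there is no loss without a cap, and the SAP calls 320 an expected value, not an assay ceiling. An added constant also keeps most of the power. Its cost is an estimate that depends on the constant.
- *Assumptions.* The shares, the power figures and the likelihood of the switch all follow from assumed, roughly log-normal titres. Steps 1 and 2 need no distribution.
- *Scope.* This is a conditional fallback for one of two primary variables. Seroconversion, on which the sample size rests, does not use it.

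A reader might infer that dropping undefined values always removes more controls and so shrinks the BCG effect. That holds only for groups 1 and 3, and only if BCG is beneficial. In group 4 both samples follow influenza vaccination, flat or falling titres are plausible, and most exclusions could fall in the treated arm.

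**Conclusion.** The point holds as a defect of the text. The fallback as written is undefined for zero or negative change, is not a fold rise where it is defined, and comes with no rule for the undefined values. It should be fixed, and doing so is nearly free.

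Its size is uncertain. Under the assumptions shown, dropping undefined values would exclude about 13–26% of controls, pull the groups 1 and 3 estimates towards no effect, and cost between nothing and about 25 points of power against the planned raw-difference analysis. For group 4 no direction can be stated.

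The documents do not support a claim that false-positive findings become more likely for groups 1 and 3, since type I error stays near 5%. Nor do they show that the analyst would in fact follow the literal wording.

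**What to change.** 1. In section 14.0, Primary outcome, replace the description of the fallback with: *change in log10 titre (log10 of the day-42 titre minus log10 of the day-14 titre), adjusted for log10 day-14 titre, age group and sex, reported as geometric mean ratios with 95% CI*. Regressing log10 day-42 titre on group and the same covariates gives the identical group estimate.
2. State one numeric value for titres below the assay's reporting limit. First reconcile the lower end of the range, <20, with the first limb of the seroconversion rule: "Seroconversion is defined as a pre-vaccination HAI titer <10 and a post-vaccination titer" of at least 40. Coding <20 as 10 is one option. It leaves the post-vaccination threshold at 40 (4 × 10), the same as coding it 5, whereas 19 would raise it to 76 (4 × 19). With 10, the <10 limb can no longer be reached, which is why the reporting limit needs clarifying first.
3. Correct the scale of ab_diff_strain in the variable list, and align Table 2 with the ratio scale.
4. Optional: make the log-titre model the lead analysis, so that no switch triggered by residuals is needed.

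The use of a post-vaccination day-14 titre as the group 4 baseline is a separate issue and should be raised on its own.

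Cost: SAP wording and table shells only. Results become ratios instead of titre differences, and they depend mildly on the value given to low titres (in the simulation at 65%, coding <20 as 5 instead of 10 adds 0.04–0.07 to the ratio).

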#### Secondary outcomes:

##### *Self-reported infections:*

The hazard ratio of infections will be estimated using an Andersen-Gill Cox proportional hazards regression model with infections included as recurrent events and time since inclusion as underlying time scale. The proportional hazards assumption will be tested using Schoenfeld residuals. As participants are only able to report one infectious episode during a follow-up questionnaire, the event will be assigned to the first day within the questionnaire period, and the following 14 days of follow-up excluded for analyses as it represents risk free time.

Association between influenza antibody titer level at day 42 and rate of infections will also be explored in Andersen-Gill Cox proportional hazards regression model, using antibody titer at day 42 as exposure and self-reported infections after day 42 as outcome. Antibody titers will be categorized into quartiles or similar relevant categories. The analysis will be adjusted for sex and age group.

Absolute risk reduction will be calculated using Cox regression.

*Immunological outcomes (subgroup analyses):*

Mean change in number of activated B-cells, concentration of cytokines, as well as fold change in cytokine concentration after stimulation from day 0 to day 14 and from day 14 to day 42 will be compared between the control group and the three treatment groups in linear regression analyses. With and without adjustment for responses in the control condition.

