## 2.0 INTRODUCTION

### Background

Severe influenza virus infections are more common in the elderly and seasonal vaccination with inactivated influenza vaccine (IIV) is recommended to persons above 65 years of age. However, due to immunosenescence, the efficacy of vaccines decrease with increasing age.

The Bacille Calmette Guérin vaccine (BCG) was developed for tuberculosis prevention, but there is increasing evidence that it also has beneficial heterologous “non-specific” effects on the immune system. Prior studies have shown that BCG vaccine strengthens the innate immune system resulting in increased activity against non-related infections. A potentiating effect of BCG vaccine on the response to other vaccines has also been observed in previous studies.

In the present project, we will explore BCG as a low-cost, low-risk intervention to increase the immune response to influenza vaccination and improve the general resistance towards infections in senior citizens.

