### Objectives and hypothesis

We will test the effects of BCG vaccination on the specific immune response to IIV and on the immune system and health in general in people  $\geq 65$  years, with the aim to:

- Improve their specific antibody response to influenza vaccination.
- Improve their general resistance towards infections.
- Study the effect of BCG on classical lymphocyte-dependent responses, and the induction of innate immune memory.

We will test the following hypotheses:

- a) BCG vaccine given two weeks prior to, together with, or two weeks after IIV is associated with a 30% increase in seroconversion to IIV and/or a significant increase in influenza antibody titers.
- b) The hypothesized potentiating effects of BCG is due to a combination of classical lymphocyte-dependent responses, and the induction of innate immune memory (trained

immunity) in myeloid cells.

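### Part B: the exploratory model of day-42 titre and later infection leaves out randomization group, which confounds the association if BCG affects both

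*SAP*

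**What the plan says.** SAP Part B, section 14.0, Secondary outcomes (Self-reported infections), specifies an Andersen-Gill model "using antibody titer at day 42 as exposure and self-reported infections after day 42 as outcome", with titre cut into quartiles or similar categories. The covariates follow: "The analysis will be adjusted for sex and age group". The Methods paragraph of the same section has analyses done "for all participants studied together and stratified by sex and age group", so arm does not enter as a stratum either. In section 13.0 the variable list gives the titre quartile as a secondary exposure, and Table 3 in section 15.0 has four quartile rows with a hazard ratio and an absolute risk reduction. Neither mentions arm.

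On what arm is expected to do, hypothesis (a) in the Part B Objectives is that BCG, at any of the three timings, "is associated with a 30% increase in seroconversion to IIV and/or a significant increase in influenza antibody titers". One of the listed aims is "Improve their general resistance towards infections". The Part B Background names both effects together: "increase the immune response to influenza vaccination and improve the general resistance towards infections in senior citizens". On sampling time, the primary outcome description in section 13.0 notes that "for group 4, it will be 2 and 6 weeks after influenza vaccination"; the other groups are sampled just before and 4 weeks after.

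**The concern.** Arm is assigned before the day-42 titre is measured. If it influences both the titre and the later infections by separate routes, it is a common cause of exposure and outcome. A separate route is plausible on the SAP's own account. Hypothesis (b) includes innate immune memory as part of the mechanism, and the outcome is any self-reported infection (vomiting and diarrhoea count), not influenza alone.

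Titre quartiles formed over the pooled arms would then partly sort participants by arm. Sex and age group cannot correct this, because randomization was stratified on them and they carry almost no information about arm. At stake is how one exploratory result is read: some apparent benefit of a high titre could belong to BCG.

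**Working it through.** The plan gives no figure for this analysis, so there is none to reproduce. The check sizes the bias when titre has no effect of its own.

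**Inputs from the SAP**
- Allocation: "Participants are randomized 1:1:1:1 to four groups" (section 10.0), so 25% control and 75% BCG.
- Control seroconversion 50%, with a 30% increase targeted (section 10.0, Sample size). The increase can be read as 50% to 65% (relative) or 50% to 80% (points).
- 300 participants with 10% loss anticipated (same place).

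**Assumptions, not in the SAP for Part B**
- Log-titre is normal with equal SD in every arm.
- The BCG titre shift d is taken from the seroconversion figures: z(0.65) = 0.385 SD and z(0.80) = 0.842 SD. Round values of 0.5 and 0.8 SD are also shown.
- The BCG infection hazard ratio h is 0.9 or 0.75, with 0.60 and 0.50 as more extreme cases. The value 0.75 borrows the 25% reduction hypothesised in Part A for a different outcome over 12 months.

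**Formula**

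The quartile cut-points q1 and q3 solve 0.25·Φ(q) + 0.75·Φ(q − d) = 0.25 and 0.75. The control shares are
- bottom quartile: c_lo = 0.25·Φ(q1) / 0.25 = Φ(q1)
- top quartile: c_hi = 0.25·[1 − Φ(q3)] / 0.25 = 1 − Φ(q3)

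The mean relative hazard in a quartile with control share c is c + (1 − c)·h. The spurious hazard ratio is [c_hi + (1 − c_hi)·h] / [c_lo + (1 − c_lo)·h].

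**Worked case, d = 0.385, h = 0.75**
- q1 = −0.394 and q3 = 0.973, so c_lo = 0.347 and c_hi = 0.165.
- Bottom: 0.347 + 0.653 × 0.75 = 0.837. Top: 0.165 + 0.835 × 0.75 = 0.791.
- Ratio: 0.791 / 0.837 = 0.95.

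**Results, top versus bottom quartile, no true titre effect**

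| Titre shift (SD) | Control share, bottom / top | h = 0.9 | h = 0.75 | h = 0.60 | h = 0.50 |
|---|---|---|---|---|---|
| 0.385 | 35% / 17% | 0.98 | 0.95 | 0.90 | 0.87 |
| 0.5 | 38% / 14% | 0.98 | 0.93 | 0.88 | 0.83 |
| 0.8 | 46% / 9% | 0.96 | 0.90 | 0.81 | 0.75 |
| 0.842 | 47% / 9% | 0.96 | 0.89 | 0.81 | 0.74 |

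With d = 0 or h = 1 the ratio is exactly 1.00.

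**Group 4 timing.** Assume that the later sample lowers group 4's titre by 0.25 SD. At h = 0.75 the ratio moves from 0.95 to 0.96 (d = 0.385) and from 0.89 to 0.90 (d = 0.842). With the timing difference alone and no BCG effect on titre, it is 1.01.

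**Does adding arm remove it?** Poisson models were fitted to 400,000 simulated participants for d = 0.385 and 0.842 and h = 0.75 and 0.50. The top-versus-bottom ratio was 0.94, 0.87, 0.89 and 0.75 without arm, and between 0.99 and 1.01 with arm.

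**Against sampling error.** 300 × 0.9 = 270 participants, or 67.5 per quartile. Assume 0.3 to 1.5 infections per person after day 42 with Poisson counts, which ignores within-person clustering and so flatters precision. The SE of the log hazard ratio is about √(2 / (67.5 × m)), where m is the mean count: 0.31 at m = 0.3 and 0.14 at m = 1.5. A spurious ratio of 0.93 (log −0.073) is then 0.2 to 0.5 SE from the null, and 0.81 (log −0.205) is 0.7 to 1.5 SE.

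**The case against.** The strongest reply is that the analysis is descriptive. Section 13.0 asks whether titres correlate with infection risk, section 14.0 calls the analysis exploratory, and Table 3 is headed as an association. A marginal association over all participants is a legitimate target and does not need arm. Sex and age group are the randomization strata used throughout Part B, so adjusting for them does not by itself show a causal aim. This has force, but it does not settle the matter. The model is already covariate-adjusted, and the table reports hazard ratios and absolute risk reductions by titre quartile, a format that invites a protective reading. Because arm precedes titre, adjusting for it does not block a true titre effect, which remains estimable within arms.

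A second reply is that adding arm still leaves an observational comparison. Prior influenza exposure, chronic disease and general immune function may influence both titre and infection. That stands, and it limits what the fix can claim.

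Two stronger readings are tempting and are not supported. A reader might infer that Part B hypothesises a reduction in infection. It does not: its two lettered hypotheses concern antibody response and mechanism, better resistance is an aim with no effect size, and the 25% figure belongs to Part A. A reader might also infer that the analysis is bound to show high titres as protective. With about 270 people, the artefact under moderate assumptions is well within sampling error.

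**Conclusion.** The omission is real: nothing in Part B puts randomization group into this model or stratifies it by arm. It biases the titre–infection association, read as an effect of titre, only if BCG both shifts titres and lowers infection by another route. Under the assumed range (0.385 to 0.84 SD, infection hazard ratio 0.9 to 0.75) the spurious top-versus-bottom hazard ratio is about 0.98 to 0.89; it reaches 0.81 at 0.8 SD and 0.60, for which the SAP gives no basis. Group 4's later sampling adds little. The bias runs towards the expected answer and grows with the strength of the BCG effects, which is why it is worth removing. Severity is minor: this is an exploratory analysis within a secondary outcome, and neither the antibody primary outcome nor the randomized infection comparison is touched.

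**What to change.** In section 14.0, add randomization group (four levels) as a covariate in the titre–infection Andersen-Gill model, or stratify the baseline hazard by group. Report the result without arm next to it in Table 3, so that the reader sees how much of the association is carried by arm. State that the result is an association, since other determinants of titre remain unadjusted. As a covariate this costs 3 degrees of freedom; it needs one sentence in the SAP and no new data.

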### **Secondary outcomes**

*Self-reported infections:*

Infections are identified through information given by the participants in the electronic follow-up questionnaires, where they are asked to describe disease episodes every 14 days. They are asked if they have been ill, and then asked to cross off their symptoms on a list. Furthermore, we ask them to provide the most likely cause for their illness. Disease episodes are characterized as infections if participants report symptoms compatible with an infectious disease or they report an infectious disease diagnose as the cause of their illness. Criteria for self-reported infection:

- Having one or more of the following symptoms: fever, cough, sore throat, runny nose/nasal congestion (common cold symptoms), loss of smell or taste sense, vomiting, or diarrhea with or without general symptoms such as headache, myalgia, dysarthria, or fatigue.
- Having dyspnea AND fever with or without general symptoms such as headache, myalgia, dysarthria, or fatigue.
- Having described an infectious disease as the self-estimated cause of illness. This is a free-text field and participants answers will be classified as infectious disease or not by medically trained study personnel.

Baseline for analysis is set at day 14 reflecting completion of the allocated vaccinations. We will however also conduct the analysis from day 0-14. Participants can register a maximum of one infectious disease event per survey period (14 days).

A secondary analysis of association between influenza antibody level and subsequent risk of infection will be performed to test if high antibody titers correlate with risk of infection.

*Immunological outcomes (subgroup analyses):*

A random subset of participants (the first to accept) have extra blood samples taken for further immunological analyses.

1. Lymphocyte-dependent responses 7 days after influenza vaccination
2. The induction of innate immune memory 14- and 42-days post-randomization

For the lymphocyte analyses, 10 participants from groups 1-3 will have blood drawn on day 21, exactly 7 days after influenza vaccination. We will assess the effect of the different treatment combinations on the response to the influenza vaccine, examining activated

influenza antibody-secreting B-lymphocytes. Due to the different timing of the influenza vaccination, participants from group 4 are not part of this analysis.

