For the trained immunity analyses, 15 participants from each group will have extra blood samples taken on day 0, 14, and 42. Peripheral blood mononuclear cells (PBMCs) are isolated from the samples and subsequently stimulated in vitro with various antigens. The immune function will be assessed by cytokine production capacity measured by Luminex technology after stimulation. The outcome measure for this analysis is concentration of different types of cytokines produced following stimulations. We will compare fold change in cytokine production between the groups at the various timepoints with and without adjustment for responses in control medium. This will allow us to determine whether BCG in the different combinations with influenza vaccine induces trained immunity in this population.

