### Figure 3: Results trained immunity.

Boxplots showing fold increase in cytokine production after stimulation with bacterial antigens and influenza vaccine at day 0, day 14, and day 42 for each treatment group.

\* Denotes within-group statistically significant change in cytokine levels between day 0 and 14 or between day 14 and 42

Δ Denotes between group statistically significant different change in cytokine levels between day 0 and 14 or between day 14 and 42

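### Part B cytokines, day 0 to 14: only Group 1 has had BCG by then, so the BCG contrast should be Group 1 against Groups 2 and 3 pooled, with Group 4 reported as influenza vaccine alone

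*SAP*

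**What the plan says.** Part B randomises 1:1:1:1 to "BCG 14 days before, together with, or 14 days after IIV compared to placebo". The schedule table in section 10.0 (Trial design) gives one injection on day 0 and two on day 14. The first two rows read "1 BCG IIV + Placebo" and "2 (Control) Placebo IIV + Placebo". Group 3 receives placebo on day 0, then IIV and BCG on day 14. Group 4 receives IIV on day 0, then placebo and BCG on day 14.

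In the trained-immunity substudy (section 13.0, Secondary outcomes), 15 participants per group are sampled on days 0, 14 and 42. Of the comparison between groups the SAP says: "This will allow us to determine whether BCG in the different combinations with influenza vaccine induces trained immunity in this population". Section 14.0 (Immunological outcomes) plans linear regressions in which changes "from day 0 to day 14 and from day 14 to day 42 will be compared between the control group and the three treatment groups". The list of variables in section 13.0 makes randomisation group a categorical exposure for fold change. The legend of Figure 3 reserves a symbol that "Denotes between group statistically significant different change in cytokine levels between day 0 and 14", or between days 14 and 42.

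Nowhere does the SAP combine Groups 2 and 3 for the first interval, restrict the BCG inference there to Group 1, or identify the Group 4 contrast as one of IIV alone.

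**The concern.** The same set of contrasts is applied to two intervals in which the groups differ in quite different ways. After day 14 every group has had all its injections, and the three BCG timings can be compared with control. Before day 14 there is no BCG timing to compare: one group has had BCG, two have had placebo, and one has had IIV.

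Day 0 to 14 is also the only interval in which BCG acts without IIV. That makes it the most direct evidence on whether BCG itself induces trained immunity, which is part of hypothesis (b). With 15 participants per group, precision is scarce. Half of the placebo-only participants are left out of the reference group and are used instead for a comparison whose true difference is zero by design.

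**Working it through.** **Exposure up to day 14, from the schedule table**

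| Contrast with Group 2 | Injection on day 0 | What it estimates over day 0 to 14 |
|---|---|---|
| Group 1 | BCG v placebo | BCG effect |
| Group 3 | placebo v placebo | zero by design |
| Group 4 | IIV v placebo | IIV effect, no BCG |

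This assumes that the day 14 blood cells are drawn before the day 14 injections. Section 13.0 says so for the antibody sample in the groups given IIV on day 14, but not explicitly for the cytokine sample. A draw later on the same day would hardly change the table.

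**Tests of a known null.** The list of variables names 3 cytokines and 4 stimuli, so Group 3 v Group 2 gives 3 × 4 = 12 tests. Section 11.0 sets two-sided significance at 0.05, so 12 × 0.05 = 0.6 false positives are expected. This expectation does not depend on correlation between the tests. It counts one version of the analysis. Section 14.0 plans both concentration and fold change, with and without adjustment for the control condition, and each version repeats the 12.

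**Precision of the BCG contrast.** The SAP gives no power figure for this substudy, so there is none to reproduce. With n = 15 per group and outcomes in SD units:

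- Group 1 v Group 2: SE = √(1/15 + 1/15) = 0.365 SD.
- Group 1 v Groups 2+3: SE = √(1/15 + 1/30) = 0.316 SD.
- Ratio 0.316/0.365 = 0.866, so the SE is 13% lower and the variance 25% lower.

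**Power in the planned regression.** Power is taken from the noncentral t distribution with noncentrality d/SE. Residual degrees of freedom are 60 − 4 = 56 with four groups and 60 − 3 = 57 after pooling. The effect d is an assumption, shown as a range.

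| Assumed effect (SD) | Group 1 v 2 | Group 1 v 2+3 |
|---|---|---|
| 0.5 | 27% | 34% |
| 0.8 | 58% | 70% |
| 1.0 | 77% | 87% |
| 1.2 | 90% | 96% |
| Detectable with 80% power | 1.04 SD | 0.90 SD |

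The four-group model already uses Group 3 to estimate the residual variance, so these figures do not credit pooling with that gain.

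**The case against.** The strongest defence is that nothing in the plan is biased. Group 1 versus Group 2 is a randomised BCG-versus-placebo comparison and it is already planned. Group 4 versus control is a legitimate estimate of an IIV effect, and Group 3 versus control could serve as a negative control. All of this stands. Pooling improves efficiency and does not correct a bias. The SAP does not, however, call Group 3 a negative control; it counts it among the treatment groups.

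A reader might infer that Figure 3 would present chance differences in Group 3, or IIV effects in Group 4, as effects of BCG timing. The document does not support that. The legend marks differences between groups without attributing them to BCG, the schedule is printed in the SAP, and Figure 2 is planned to show the vaccination timeline. The sentence on BCG in its different combinations also covers day 42, when every combination is complete. What remains is that the figure would carry marks of three different meanings under one symbol.

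A reader might also put the chance of at least one false positive among the 12 tests at 1 − 0.95¹² = 46%. That requires independent tests, which is unlikely for cytokines measured in the same participants' cells. Only the expected 0.6 should be relied on.

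For infections, section 13.0 says only "We will however also conduct the analysis from day 0-14". Analysis by randomised group is the natural reading, but it is not stated, and Table 3 has no row for that interval. The main infection analysis starts at day 14, so the same problem does not arise there.

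An appeal to intention-to-treat would not be a reason against pooling. Groups 2 and 3 were both randomised and were assigned identical treatment up to day 14.

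**Conclusion.** The point holds for the Part B cytokine outcomes over day 0 to 14. Of the three planned contrasts, only Group 1 versus control can show a BCG effect. That contrast is valid but less precise than the available data allow: its SE is 0.365 rather than 0.316 SD, and its detectable difference 1.04 rather than 0.90 SD. Group 3 versus control contributes 12 tests of a known null per version of the analysis.

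The figures assume 15 evaluable participants in each group, equal variances and no gain from covariates. The power values also rest on assumed effect sizes.

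This is a secondary analysis in a subset. The point does not touch the primary antibody outcome or the cytokine comparison over day 14 to 42. It does not apply to activated B-cells either, which are sampled only on day 21 and only in Groups 1 to 3. For the day 0 to 14 infection analysis it applies only if that analysis is run by randomised group.

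**What to change.** In section 14.0 (Immunological outcomes), define the day 0 to 14 cytokine contrasts by what had been given on day 0:

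- BCG effect: Group 1 versus Groups 2 and 3 pooled.
- IIV-alone effect: Group 4 versus the same pooled placebo group, reported under that name.
- Group 3 versus Group 2: not tested as a treatment contrast. If it is shown at all, label it a placebo-placebo check.

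Keep the four-group comparison for day 14 to 42. In Figure 3, let the between-group symbol for day 0 to 14 refer only to the first two contrasts, with a note on which is which, and mark no Group 3 versus control difference as a treatment effect.

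In section 13.0, state the grouping for the day 0 to 14 infection analysis. If it is by randomised group, use the same pooling.

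The cost is a few lines of SAP text and one recoded group variable for the first interval. No samples, participants or trial procedures change.
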